Annex 4. NCI-CTCAE criteria

The common terminology criteria for the classification of adverse events version 5.0 (NCI-CTCAE v. 5.0) can be consulted at the following Internet address:

https://ctep.cancer.gov/protocolDevelopment/electronic_applications/docs/CTCAE_v5_Quick_Reference_8.5x11.pdf

Annex 5. Post-COVID complications

	List of post-COVID complications		
COMPLICATIONS	HAVE HAD	Duration	Worst grade
Fatigue/asthenia	YES/NO	Start/end date	
General malaise	YES/NO	Start/end date	
Headaches	YES/NO	Start/end date	
Low mood	YES/NO	Start/end date	
Muscle aches and pains	YES/NO	Start/end date	
Joint pains	YES/NO	Start/end date	
Attention deficit	YES/NO	Start/end date	
Chest pressure	YES/NO	Start/end date	
Anxiety	YES/NO	Start/end date	
Febricula	YES/NO	Start/end date	
Cough	YES/NO	Start/end date	
Memory lapses	YES/NO	Start/end date	
Diarrhoea	YES/NO	Start/end date	
Palpitations	YES/NO	Start/end date	
Dizziness	YES/NO	Start/end date	
Tingling in extremity	YES/NO	Start/end date	
Others (specify)	YES/NO	Start/end date	

List based on the survey carried out by the Spanish Society of General Practitioners and Family Doctors.

Annex 6. Barthel Index

ÍNDICE DE BARTHÉL

	Con ayuda	De forma independiente
1. Alimentarse (si es preciso trocear la comida = ayuda)	5	10
2. Pasar de la silla de ruedas a la cama y volver a la silla (implica poder sentarse en la cama)	5-10	15
3. Aseo personal (lavarse la cara, peinarse, afeitarse, cepillarse los dientes)	0	5
4. Sentarse en el inodoro y levantarse (manejar la ropa, limpiarse, tirar de la cadena)	5	10
5. Lavarse	0	5
6. Caminar sobre una superficie plana (o bien impulsar la silla de ruedas, si es incapaz de caminar)	10 0*	15 5*
*Solamente se debe puntuar si el paciente es incapaz de caminar		
7. Subir y bajar escaleras	5	10
8. Vestirse (incluye atarse los cordones de los zapatos, cerrar cremalleras, broches y otros cierres)	5	10
9. Control de las deposiciones	5	10
10. Control de la micción	5	10

Annex 7. Dyspnoea scale mMRC (modified Medical Research Council)

Grade Severity of symptom

0	I only get breathless with strenuous exercise
1	I get short of breath when hurrying on level ground or walking up a slight hill
2	On level ground, I walk slower than people of the same age because of breathlessness, or have to stop for breath when walking at my own pace
3	I stop for breath after walking about 100 metres or after a few minutes on level ground
4	I am too breathless to leave the house or I am breathless when dressing

doi: 10.1378/chest.93.3.580. PMID: 3342669.*

Annex 9 Instructions for the 6 minute walk test.

See article and erratum in separate documents.

ATS Committee on Proficiency Standards for Clinical Pulmonary Function Laboratories. ATS statement: guidelines for the six-minute walk test. Am J Respir Crit Care Med. 2002 Jul 1;166(1):111-7. doi: 10.1164/ajrccm.166.1.at1102. Erratum in: Am J Respir Crit Care Med. 2016 May 15;193(10):1185. PMID: 12091180.

APPENDIX

The following elements should be present on the 6MWT worksheet and report:

Lap counter: _____

Patient name: _____ Patient ID# _____

Walk # _____ Tech ID: _____ Date: _____

Gender: M F Age: _____ Race: _____ Height: _____ ft _____ in, _____ meters

Weight: _____ lbs, _____ kg Blood pressure: _____ / _____

Medications taken before the test (dose and time): _____

Supplemental oxygen during the test: No Yes, flow _____ L/min, type _____

	Baseline	End of Test
Time	____:____	____:____
Heart Rate	_____	_____
Dyspnea	_____	_____ (Borg scale)
Fatigue	_____	_____ (Borg scale)
SpO ₂	_____ %	_____ %

Stopped or paused before 6 minutes? No Yes, reason: _____

Other symptoms at end of exercise: angina dizziness hip, leg, or calf pain

Number of laps: _____ (×60 meters) + final partial lap: _____ meters =

Total distance walked in 6 minutes: _____ meters

Predicted distance: _____ meters Percent predicted: _____ %

Tech comments:

NCI-CTCAE	National Cancer Institute-Common Terminology Criteria for Adverse Events
PaFi (PAO ₂ /FiO ₂) Ratio	Ratio of partial pressure arterial oxygen and fraction of inspired oxygen
PCR	Polymerase chain reaction
PR	PR interval
PT	Preferred term
Q1	First quartile
Q3	Third quartile
QT	QT interval
RR	Respiratory rate
SAE	Serious adverse event
SaO ₂	Oxygen saturation
SARS-CoV-2	Severe acute respiratory syndrome coronavirus 2
SAS	Statistical analysis system
SAEs	Serious adverse events
SBP	Systolic blood pressure
SOC	System organ classes
Std	Standard deviation
ULN	Upper limit of normal
WHO	World health organization
WBC	White blood cell

2 Synopsis

2.1 Title of the study

Extension study in a cohort of adult patients with severe acute respiratory syndrome coronavirus 2 (SARS-CoV-2) infection requiring hospital admission who received treatment with plitidepsin in the APLICOV-PC.

2.2 Justification of the study

The APLOCOV-PC proof of concept study demonstrated the antiviral activity of plitidepsin in terms of viral load reduction, recovery induction, lymphocyte and other inflammatory parameters reconstitution.

Approximately 10 to 25% of patients with COVID-19 experience symptoms beyond 3 months, resulting in a significant restriction in their everyday lives due to the sequelae of the disease that may persist for a year or more and entail long-term medical leaves.

The aim of this study is to assess whether the treatment with plitidepsin, by attaining a reduction in the viral load and a faster recovery of the patient, could have a relevant impact in preventing the appearance of sequelae resulting from the SARS-CoV-2 infection.

23 Code of the study

E-APLOCOV-PC (AV-APL-A-003-21).

24 Sponsor

Pharma Mar, S.A

25 Design

Multi-site extension study of the APLOCOV-PC clinical study follow-up.

To participate in the study, the patients must have previously participated in the APLOCOV-PC proof of concept study and may have received:

- 1.5 mg of plitidepsin administered as a 1.5-hour infusion, once a day for 3 consecutive days (total dose 4.5 mg).
- 2.0 mg of plitidepsin administered as a 1.5-hour infusion, once a day for 3 consecutive days (total dose 6.0 mg).
- 2.5 mg of plitidepsin administered as a 1.5-hour infusion, once a day for 3 consecutive days (total dose 7.5 mg).

Patients were enrolled after signing informed consent to participate in this extension study.

26 Study Objectives

To evaluate the incidence of post-COVID-19 morbidity and characterize the profile of complications in patients who participated in the APLOCOV-PC study.

27 Endpoints

Incidence of post-COVID-19 complications.

28 Study population

The main objective of the study is to evaluate the incidence of post-COVID-19 morbidity and

characterize the profile of complications in patients who participated in the APLICOV-PC study. The maximum number of patients who can participate in the trial is limited to 42.

2.9 Inclusion criteria

Patient who participated in the APLICOV-PC study treated with plitidepsin and who gives their consent.

2.10 Exclusion criteria

There are no exclusion criteria for this study.

3 General principles

Planned analyses in this document will be carried out once the database is declared cleaned, closed and approved by Pharma Mar according to the premises described in the Data Management Plan version 1.0 approved on 12-Jan-2022.

Statistical analyses will be performed using Statistical Analysis System (SAS) software version 9.4 and RStudio. The results of the analyses will be presented in editable format (i.e. rtf).

The data will be provided with one decimal place in general. In those cases where greater precision is required, as many decimal places as necessary will be provided.

Before performing the analysis, the following terms should be coded/reviewed and approved:

- Adverse events (AEs), hospital readmissions and COVID-19 complications. Coded according to Medical Dictionary for Regulatory Activities (MedDRA) and graded according to the National Cancer Institute Common Terminology Criteria for Adverse Events (NCI-CTCAE) v5.
- Medication. Classified according to the WhoDrug dictionary (latest version available).
- Reconciliation between the clinical database and the Pharmacovigilance database of serious adverse events (SAEs) in the study, including the resolution of all discrepancies.

Analysis will be done separately for each arm and the total population.

Continuous variables will be presented through the mean, median, standard deviation, range, first quartile (Q1) and third quartile (Q3). Categorical variables will be displayed through the distribution of frequencies and percentages; percentages with valid data will be presented and missing values will not be taken into account in the percentage calculation.

4 Imputation

There is no strategies/methods to handle missing data.

5 Study analysis populations

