1.11. Endpoints

Incidence of post-COVID-19 complications.

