12. STATISTICAL CONSIDERATIONS

12.1. General considerations

This section describes the main analyses that will be carried out. The statistical analysis plan to be approved by the sponsor will include additional information on analyses, management of unavailable data and analytical methods. All data will be analysed with the SAS statistical analysis system, version 9.4. All analyses will be carried out mainly by descriptive statistical methods. Continuous endpoints will be described using maximum, minimum, Q1 and Q3, mean, median and standard deviation. Categorical endpoints will be described with frequencies and percentages as well as the exact 95% confidence interval of the relevant study variables. All results will be presented separately by treatment arm and severity of the information upon entry into the APLICOV-PC study.

The final statistical study that will be the basis of the study's final report, will cover the total population of patients once the extension study has ended.

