12.2. Sample size

The main objective of the study is to evaluate the incidence of post-COVID morbidity and characterize its profile in patients who participated in the APLICOV-PC study. Given that a total of 45 patients received plitidepsin in said study, of which 3 died as a consequence of the progression of the disease, the maximum number of patients who could participate in the study is limited to 42.

Assuming an average incidence of post-COVID complications of 15%, this study would have a power of 80% for detecting a reduction of 10%: if 3 or less patients presented post-COVID complications, the study would reject the null hypothesis (incidence of post-COVID complications: 15%) and would accept the alternative (5%), with an alpha error of 0.05 (unilateral).

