6.2 Patients characteristics

Demographic and baseline data:

- Age (years)
- Gender (male/female)
- Ethnic group (Arab; Caucasian; Latin; Asian; Black; Other)
- Weight (kg)
- Height (cm)
- Body surface area (BSA) (m²)
- Body mass index (BMI) - calculated

In addition to all the basal characteristics used in APLICOV-PC if it necessary.

7 Analysis of the primary endpoint

The main objective of the study is to evaluate the incidence of post-COVID-19 morbidity and characterize the profile of complications in the cohort of patients who participated in the APLICOV-PC study.

The number and percentage of patients who develop complications related to persistent illness, according to the physician, during the period between the end of the APLICOV-PC proof of concept study and the completion of this extension study by the patient, as well as the percentage of patients who present complications will be detailed.

A description of the following endpoints will be presented:

- Number and percentage of patients who required readmission to hospital and causes, since last visit of APLICOV-PC study until the end of this extension study.
- Number and percentage of patients who needed oxygen therapy and duration of the same, since last visit of APLICOV-PC study until the end of this extension study.
- The maximum, minimum, Q1 and Q3, mean, median and standard deviation (Std) of the duration of the oxygen therapy.
- Number and percentage of patients who presented complications (defined in Annex 5 of the protocol).
- Barthel Index. A description with the frequency and percentage of each dependency category, according to the score obtained, will be provided:
 - 0-20: Total dependency
 - 21-60: Severe dependency
 - 61-90: Moderate dependency
 - 91-99: Slight dependency
 - 100: Independence
- The maximum, minimum, Q1 and Q3, mean, median and Std of the parameters related to pulmonary function will be provided: oxygen saturation (SaO₂), ratio of partial pressure arterial oxygen and fraction of inspired oxygen (PAFI), forced vital capacity (FVC), forced expiratory volume in 1 second (FEV1), FEV1/FVC and diffusion test.

- The maximum, minimum, Q1 and Q3, mean, median and Std of the results of the Six-minute walk test (6MWT).
- Frequency and percentage of each category of the modified Medical Research Council (mMRC) scale:
 - 0 (Dyspnea only after strenuous exercise)
 - 1 (Dyspnea occurring when hurrying on level ground or walking up a slight incline)

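### The 3-or-fewer rule in protocol 12.2 has a one-sided error rate of 0.107 at N=42, not 0.05; the SAP neither applies nor withdraws it, and its tables omit the exact 95% interval promised in protocol 12.1

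*SAP*

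**What the plan says.** **Endpoint.** Protocol 1.11 gives one endpoint, "Incidence of post-COVID-19 complications". Section 6.2 words it as complications related to COVID-19 infection, and section 6.3 says secondary outcomes are not applicable.

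**Precision.** Protocol 12.1 states: "Categorical endpoints will be described with frequencies and percentages as well as the exact 95% confidence interval of the relevant study variables". The same section says "All analyses will be carried out mainly by descriptive statistical methods" and leaves further detail to the SAP.

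**Decision rule.** Protocol 12.2 takes 15% as the average incidence and 5% as the alternative, with at most 42 patients (45 treated minus 3 deaths). It says that "if 3 or less patients presented post-COVID complications, the study would reject the null hypothesis", with one-sided alpha 0.05 and power 80%. Section 8.2 rules out replacing patients who decline or withdraw.

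**SAP.** Section 3 (General principles) says of categorical data: "Categorical variables will be displayed through the distribution of frequencies and percentages; percentages with valid data will be presented". Section 7 (Analysis of the primary endpoint) opens with "The number and percentage of patients who develop complications related to persistent illness, according to the physician" and continues "as well as the percentage of patients who present complications will be detailed". Tables 11.1.1 (by dose) and 11.1.2 (by severity) have n (%) columns and three complication rows: related or unknown relationship, regardless of relationship, and related. The only confidence limits in the SAP are for odds ratios, in Table 11.13. The SAP does not mention the 15% or 5% reference values, the cut-off or an alpha level. Its history of changes withdraws neither the rule nor the interval.

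**The concern.** There are two separate problems.

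First, the protocol contains a numerical decision rule whose stated error rate looks too low for 42 patients. The SAP, where one would expect it to be carried forward or dropped, is silent. While the rule stands, 3 of 42 could be described as rejecting 15% at a one-sided 5% level when the chance of that result or a lower one under 15% is about twice as large.

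Second, a programmer working from the SAP shells would produce a bare percentage for the only endpoint. In a cohort of at most 42, that hides how weakly the incidence is determined, which is what the protocol's promise of an exact interval was meant to show.

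**Working it through.** **Inputs.** From protocol 12.2: null p0 = 0.15, alternative p1 = 0.05, N at most 42, reject if X ≤ 3, one-sided alpha 0.05, power 80%. From protocol 5.2: a 10-25% background range of patients with persisting symptoms.

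**1. The plan's own figures.** X is binomial(N, p).

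- Alpha = P(X ≤ 3 | 42, 0.15) = 0.0011 + 0.0080 + 0.0291 + 0.0685 = 0.1067. Stated: 0.05.
- Power = P(X ≤ 3 | 42, 0.05) = 0.1160 + 0.2564 + 0.2766 + 0.1941 = 0.8431. Stated: 80%.

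Neither figure is reproduced.

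**2. Could another reading give them?** With N=45 (all treated), cut-off 3 gives alpha 0.0785 and power 81.3%. Reading 10% as a relative reduction (p1 = 0.135) gives power 16.3%. A one-sided normal approximation needs N=60. At 3/42 the Wald p-value is 0.024 and the arcsine p-value 0.0497, which may be where the cut-off came from. They do not change the rule's actual error rate of 0.107.

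**3. Other cut-offs at N=42.**

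| Reject if X ≤ | Alpha (p=15%) | Power (p=5%) |
|---|---|---|
| 1 | 0.009 | 37.2% |
| 2 | 0.038 | 64.9% |
| 3 | 0.107 | 84.3% |
| 4 | 0.225 | 94.3% |

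No row has alpha ≤ 0.05 together with power ≥ 80%. A search over all smaller N finds no such design either. The smallest N that meets both is 59 (cut-off 4, alpha 0.0469, power 82.8%), above the ceiling of 42.

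**4. Fewer than 42 analysed.** The documents do not give the number analysed. If it is below 42, alpha for a cut-off of 3 rises: 0.130 at N=40 and 0.191 at N=36. So 0.107 is the lowest value it can take in this study. If N is assumed to be between 30 and 39, an exact 5% test needs 1 or fewer events and has power between 55% (N=30) and 41% (N=39).

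**5. What the promised interval would show.** Exact (Clopper-Pearson) two-sided 95% limits at N=42:

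| Events | Percentage | 95% CI |
|---|---|---|
| 2 | 4.8% | 0.6-16.2% |
| 3 | 7.1% | 1.5-19.5% |
| 4 | 9.5% | 2.7-22.6% |
| 5 | 11.9% | 4.0-25.6% |
| 6 | 14.3% | 5.4-28.5% |
| 7 | 16.7% | 7.0-31.4% |
| 8 | 19.0% | 8.6-34.1% |
| 9 | 21.4% | 10.3-36.8% |

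The intervals for 5 to 8 events contain both 10% and 25%; those for 4 and 9 do not.

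**6. Which limit matches a one-sided test.** The one-sided 95% upper limit is 14.2% for 2/42 and 17.4% for 3/42, so it separates the two counts at 15%. The two-sided 95% interval does not, because both contain 15%.

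**The case against.** **The study is descriptive.** The rule appears only under Sample size. Protocol 12.1 calls the analyses mainly descriptive, and neither protocol 12.4 nor the SAP schedules a test against 15%. This stands. A reader might infer that the study will run a test at twice its nominal level; the documents do not support that. What remains is a wrong statement in the protocol that nothing withdraws. It can be misused because 12.2 is written as a reject-or-accept rule, and 5.2 says the study is meant to evaluate whether plitidepsin affects sequelae.

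**SAP silence does not cancel the interval.** This is also fair. Section 12.1 expects the SAP to add detail, and nothing in the SAP revokes the promise, so this is an omission rather than a contradiction. Section 12.1 also limits the interval to relevant variables without naming them, but the only endpoint must be one. The shells still leave no place for it.

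**Three complication rows.** A reader might infer that the sponsor is free to hold whichever row is lowest against the cut-off. That goes too far. Protocol 6.2 defines the endpoint as related to COVID-19 infection, and the lead sentences of 12.4 and SAP 7 start with physician-judged related complications, so the documents lean towards a relatedness-based row. The open questions are how unknown relationship is counted and what the trailing clause on all patients with complications adds. They affect the rule only if a test is kept.

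**The date of the SAP changes.** A reader might see 17 November 2022, set against inclusion planned to end in December 2021, as a sign of choices made after seeing data. The documents do not show this. The tables listed as added include 11.1.2 but not 11.1.1, and no database lock date is given.

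**Conclusion.** Both parts hold and should be corrected. At N=42 the 12.2 rule has exact one-sided alpha 0.107 and power 84.3%, against the stated 0.05 and 80%, and no cut-off at 42 or fewer patients delivers both. This rests only on the protocol's own inputs and the binomial model. The number actually analysed is unknown, and a smaller number makes alpha for a cut-off of 3 worse. The practical harm is conditional: it arises only if a count such as 3/42 is reported against the rule.

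The missing interval is a gap between protocol 12.1 and SAP 3, SAP 7 and Tables 11.1.1 and 11.1.2. If all 42 are analysed, any count from 5 to 8 leaves the whole 10-25% background range inside the interval, and n (%) alone would not show that.

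**What to change.** 1. Add the exact two-sided 95% confidence interval to the complication-incidence rows of Tables 11.1.1 and 11.1.2, at least in the Total column, and say so in SAP 3 or 7.

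2. Choose one of the following, write it into SAP 7, and bring protocol 12.2 into line.
   - State that the study is descriptive and that the 15% versus 5% rule is withdrawn. This fits protocol 12.1 and 12.4 and needs no choice of row.
   - Keep a test, restated as an exact one-sided binomial test against 15% at the number actually analysed and reported with the one-sided 95% upper limit. At N=42 the cut-off is 2 or fewer, alpha 0.038 and power 64.9%.

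3. Only if the test is kept, reconcile protocol 1.11, 6.2 and 12.4 with SAP 7 and name one row, including how unknown relationship is counted. Check that the row matches the event behind the 15%, for which 12.2 gives no source, and report the other rows as sensitivity analyses. Dating the decision and recording whether data had been seen would be good practice.

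**Cost.** SAP wording, interval entries in two tables, and a correction or withdrawal in protocol 12.2; no new data. The price is a visibly wide interval and either no formal test or a lower stated power: 64.9% at N=42, or 41-55% if 30 to 39 are assumed to be analysed.

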5.1 Definition of the study population to be analyzed

All patients who sign an informed consent form and agree to undergo the set of clinical examinations, imaging and laboratory tests specified in section 10 of the protocol, will be analyzed in order to fulfil the objectives of the study.

5.2 Patients disposition

The number and percentage of patients per center will be provided.

All analysis will be performed separately for each arm and a total column will be added.

5.3 End of treatment

There is no end of treatment for this study as no treatment doses are administered.

5.4 End of study

The number and percentage of patients who completed or not the study will be provided. For those patients who finished the study early, the causes of termination will be described.

The cases considered as early termination are:

- Withdrawal of consent
- Follow up completed
- Lost to follow-up
- Death
- Other

All analysis will be performed separately for each arm and a total column will be added.

5.5 Deaths

The number and percentage of patients who died during the study will be provided. Patients who have died due to an AE will be described in more detail, indicating all the variables related to the AEs registered in the electronic case report form (eCRF).

All the analyses will be performed separately for each arm and a total column will be added.

6 Patients description

6.1 Demographic data description. General considerations.

The characteristics of the patients will be described and the unavailable information will be detailed; not available values will not be taken into account in the percentage calculation, only valid percentages will be presented. The analysis will be carried out on the full population and all results will be provided by treatment arm. Aggregated results as well as patient listings will be provided.

